Prior to the baseline imaging task scan, subjects are familiarized with the 2 instructional conditions by the experimenter, using standardized scripts for the treatment and control conditions. Subjects in both conditions will be instructed that in the "Look" condition, they should simply look at the picture and be aware of whatever spontaneous emotions arise. For those in the CRD treatment group, training for the "Regulate" condition consists of two parts. First, the subjects will read a brief description of the distancing strategy. The following description of the strategy in lay language is presented: "view the photos in a very neutral way, knowing that you are not personally involved, and/or imagine that the pictured events happened far away or a long time ago. As you view each pictured event, what is important is that you cut all personal ties to the event in a way that any negative emotional reaction is decreased as much as possible." In our experience, BPD subjects readily understand the strategy explained in this way. Subjects will next practice distancing to a series of IAPS slides, not subsequently used in the scanning sessions. The experimenter will have the subject describe aloud how he/she implements distancing, slide-by-slide, and will assist the subject to shape effective strategies. The subject will next practice the distancing task in a block of 20 trials presented outside the scanner on a laptop computer. The training for subjects in the downregulate (CD) control group will be the same, except that subjects will be instructed that when they see the "Regulate" prompt they should use whatever emotion regulation strategy works for them to reduce their negative feelings. As for the treatment group subjects, the researcher will shape their behavior in 5 trials, having them draw upon their experience, and they will practice for 20 trials outside the scanner before beginning the imaging task. Subjects will be specifically instructed not to close their eyes or look away from the images in any of the conditions.

C.2.6. Distancing-Training and Downregulate Control Condition in R61 and R33 Phases

Training in distancing and in the suppression-control condition will be the same in both R61 and R33 phases, except that in the R33 phase only a single dose, the optimal dose (number of sessions) determined in the R61 phase will be employed.

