C.4.1.2. Exclusion Criteria. Subjects will not meet criteria for Schizotypal Personality Disorder (SPD). SPD is excluded to avoid a possible confound from the restricted affect that characterizes SPD. BPD subjects will not meet DSM-5 criteria for past or present bipolar I disorder, schizophrenia, schizoaffective disorder, substance dependence, organic mental syndromes, head trauma, CNS neurological disease, or seizure disorder. Subjects currently meeting DSM-5 criteria for PTSD will be excluded, unless they are in remission or not currently experiencing symptoms. Subjects currently meeting criteria for major depressive disorder will also be excluded (except as described above). However, since depression is commonly associated with BPD (Koenigsberg et al., 1999), too stringent a depression exclusion criteria would yield a clinically atypical BPD sample. For this reason, BPD patients with Axis I depressive disorders other than major depression and those with a past history of major depression, will not be excluded. Suicidal subjects will not be excluded, unless referral to a higher level of care is deemed clinically necessary by the evaluating clinician. Subjects must not have met criteria for a substance use disorder for 6 months prior to entry into the study. All subjects must be free of significant medical illness. They may not have a pacemaker, surgical clips, any metallic implants, or shrapnel fragments that would contraindicate MRI scanning. Pregnant women will be excluded.

C.4.2. Sample Size, Recruitment and Assessment

C.4.2.1 Sample Size. R61 Phase: (see Power Analysis C.4.5.1). 49 BPD subjects will be recruited each for the training and control groups to acquire 39 subjects in each group allowing for a 20% loss for drop out and fMRI movement artifact. R33 Phase: 65 BPD subjects will be recruited each for the training and control groups to obtain 51 subjects per group, allowing for 20% loss.

C.4.2.2 Recruitment:
Subjects will be recruited
by newspaper, radio,
and social media
advertisements and by
referral from the
psychiatry outpatient
department at Mount
Sinai Medical Center, the
Center for the Intensive
Treatment of Personality
Disorders at Mount Sinai
West, and the Bronx VA
Medical Center. We are
confident that we can
meet recruitment goals
for both R61 and R33 as
our Mood and
Personality Disorders
Research Program at
Mount Sinai, which has
been engaged in
neurobiological research
studies of BPD for over

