instruments (Table 1). Subjects will receive a medical evaluation (see Table 1) and will be randomized (1:1) to CRD training or CD control conditions using a randomization scheme in random blocks of 2, 4 and 6. An online, electronic randomization system will be implemented by the study statistician. The medical evaluation will take place at the Clinical Research Unit (CRU) ([name]). This will include routine blood tests (complete blood count, metabolic and electrolyte panel, thyroid function tests, and a routine urinalysis. The urine drug screen will be administered in our office ([name]) on the day of your Medical Evaluation. On a separate day, subjects will carry out the baseline imaging task (see C.2.6). For R61 Phase: Within about 2 weeks of baseline scan, subjects will begin the manualized CRDtraining or control CD training, which will continue for 6 weeks. At 2-, 4- and 6- weeks, subjects will receive an fMRI scan similar to the baseline scan (different image sets will be employed for each scan, counterbalanced for sequence among scans across subjects) and the assessment measures as indicated in Table 1. For R33 Phase: The procedures will be as in the R61 phase except that training will last for 6 weeks. Following the last session, subjects will receive the termination assessments, including fMRI, as indicated in Table 1. Subjects will return approximately 1- and 4- months after their last session for follow-up (see Table 1).

C.4.3.2 Regulation-Training Procedures, Adherence Assessment and Refinement of the Treatment Manuals for both R61 and R33 Phases

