C.5.1 R61 Phase. Analyses for Aims R61-2a and R61-2b are described in image analysis (C.6.4, below). Aim R61-2c: Data will be checked for normality and appropriate transformations will be applied to normalize them. Data analysis will primarily use linear mixed models, incorporating fixed effects for Training Group (CRD and ES), Session, and Trial Type (Look Neutral, Look Negative, and Regulate Negative), and their interactions, as well as a random effect consisting of an intercept for each participant. We will examine additional models that incorporate and estimate random-effects slope variance across participants on the time effect (i.e., Session). Outcome variables will be repeated measures in self-reported negative affect and reappraisal success (defined as the Look Negative minus Regulate Negative behavioral valence rating at each Session). Although we do not anticipate large differences in

baseline characteristics between the groups, given that the trial is randomized, we will include variables that are strongly unbalanced at baseline (p< 0.01) as covariates in our models.

C.5.2 R33 Phase. Aim R33-1: The primary outcome measure is the Zanarini total score (ZTS;[57]). We compare the change in ZTS from baseline to end of treatment (EOT) between groups by mixed effect models with group, time and their interaction as fixed effects. A similar analysis will be carried out for the additional outcome measures specified in C.3.3. (Table 1), using the Holm's procedure for correction for multiple comparisons. Aim R33-2: The analysis will be as for R61 Aims R61-2 a,b and c. Aim R33-3: The analysis is described in imaging analysis section C.6.3. Aim R33-4: As above, we will use linear mixed models to examine change in ZTS as the outcome variable. Bonferroni corrections will be applied for multiple clinical outcome measures. P-values throughout will be 0.05, two tailed. All analyses will be conducted according to the intent-to-treat principle for both the R61 and the R33 phase. As a sensitivity analysis we will also consider models that adjust for the number of sessions actually received. Missing data will be assumed as MAR. Under this assumption, a mixed model approach that uses all available information will yield reasonable estimates of the effect sizes.

C.6. Image Acquisition and Analysis

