Subjects who express interest in the study will receive a phone pre-screening evaluation, followed by a screening evaluation by [name] (PI) or a designated colleague. Research-eligible candidates will approached by a research MD or a delegate trained by him for consent to participate. Consent will be obtained after the potential subject has expressed interest in participating and after the study has been explained to the subject by the researcher. Consents will be obtained at the Icahn School of Medicine at Mount Sinai or the James J Peters VA Medical Center in a private office setting by the principal investigator or a delegate approved by the Mount Sinai and/or JJPVA IRBs. After the protocol is described to the subject and the subject's questions are answered, the subject will be asked to summarize the procedures that he/she will undergo and to describe 2 risks involved in the study to confirm understanding. A

checklist will be used for this purpose by the person obtaining consent. Informed consent will be documented by means of an informed consent form approved by the Mount Sinai and/or James J Peters VA IRBs and signed by the subject and the researcher who obtains the consent. BPD subjects are cognitively intact and have no impairment in reality testing, however, if there is any doubt about a BPD subject's capacity to give consent, a psychiatrist independent of the study will assess the subject to determine whether they understand the study and can give informed consent.

F.1.2 Protection against Risks

Should a subject become anxious or have a claustrophobic reaction in the scanner, a member of the research team will be available to reassure them and aid them in relaxing. Subjects will be informed that the scanning will be stopped immediately should they wish it. Subjects are prescreened at two points in time – when they sign the informed consent and again just prior to scanning – to insure they have no metallic implants. Women will receive a pregnancy test to exclude subjects who are pregnant. Trained technicians will draw blood, using sterile technique to minimize risk of bruising or infection the structural MRI scans of all subjects will be routinely reviewed by a neuroradiologist at the Mount Sinai Hospital and subjects will be informed of clinically significant incidental findings. If indicated, we will refer them for medical or neurological follow-up.

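### Randomisation is placed with the medical evaluation and the baseline scan on another day, so a patient lost in between is allocated but cannot supply the R61 primary outcome; a later randomisation call would avoid most of this at little cost.

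*Combined protocol and SAP*

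**What the plan says.** **Order of steps (C.4.3.1).** Randomisation shares a sentence with the medical evaluation: "Subjects will receive a medical evaluation (see Table 1) and will be randomized (1:1) to CRD training or CD control conditions". After the blood tests and drug screen are described, the text continues: "On a separate day, subjects will carry out the baseline imaging task". No maximum interval is set between allocation and that scan.

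**MRI eligibility (C.4.1.2 and F.1.2).** The exclusion reads: "They may not have a pacemaker, surgical clips, any metallic implants, or shrapnel fragments that would contraindicate MRI scanning". Metal is checked twice: "when they sign the informed consent and again just prior to scanning". For pregnancy, F.1.2 says: "Women will receive a pregnancy test to exclude subjects who are pregnant". It gives no time for the test, which appears neither among the C.4.3.1 medical tests nor in Table 1.

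**The baseline task depends on the arm (C.2.5).** "Prior to the baseline imaging task scan, subjects are familiarized with the 2 instructional conditions by the experimenter, using standardized scripts", with a separate script for each arm. The Regulate cue means distancing in one arm and the patient's own strategy in the other.

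**Outcome and analysis.** C.6.3 forms the R61 contrasts at weeks 2, 4 and 6, each against week 0. C.6.4 compares them between arms by two-sample t-tests and rests the decision to proceed to R33 on the PINES result. C.5.2 adds: "All analyses will be conducted according to the intent-to-treat principle for both the R61 and the R33 phase".

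**Loss allowance (C.4.2.1).** In R61, 49 are recruited per arm to retain 39. The 20% covers attrition and motion artefact.

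**The concern.** On the order as written, a gap lies between allocation and the baseline scan. A patient can withdraw in that gap, fail the second metal check or, depending on when the test is done, be excluded for pregnancy. That patient belongs to an arm but has no week-0 scan, so no PINES change can be formed at any dose.

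The intent-to-treat statement does not solve this. C.5.2 relies on mixed models under a missing-at-random assumption, but the PINES comparison is a t-test on within-person contrasts and cannot use someone without a baseline. No rule says how such patients are counted or reported.

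Two things are at stake. One is a small, avoidable loss of patients from the comparison that decides whether R33 goes ahead. The other is that exclusion after allocation leaves a route by which the arms could come to differ. Only the assessors are stated to be blind (C.4.2.3).

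**Working it through.** **1. Is the order fixed by the text?**
- Allocation must come before the baseline scan, because the preparation and the Regulate instruction differ by arm (C.2.5).
- The only stated placement of allocation is with the medical evaluation, and the scan is on another day (C.4.3.1).
- The first metal check is at consent and therefore before allocation. The second is just before scanning and therefore after it.
- The timing of the pregnancy test relative to allocation is not stated.

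**2. Reproducing the planned R61 size.** Inputs from C.7 and C.4.2.1: d = 0.65, two-sided alpha 0.05, power 0.80, 20% loss. For a two-sample t-test with n per arm, power comes from the noncentral t distribution with 2n − 2 degrees of freedom and noncentrality d × √(n/2).
- Solving for power 0.80 gives n = 38.14, rounded up to 39, as stated.
- Inflating for loss: 39 / 0.80 = 48.75, rounded up to 49, as stated.
- Power at n = 39: noncentrality 0.65 × √19.5 = 2.87, power 0.81.

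**3. Effect of extra loss before the baseline scan.** The documents give no rate, so f below is an assumption. The calculation takes the case least favourable to the plan, in which these losses come on top of the full 20%: analysable n per arm = 49 × 0.80 × (1 − f). The number to randomise per arm to keep 39 is 39 / (0.80 × (1 − f)), rounded up.

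| Assumed f | Patients of 98 | Analysable per arm | Power, single test | Randomised per arm to keep 39 |
|---|---|---|---|---|
| 0 | 0 | 39.2 | 0.81 | 49 |
| 2% | about 2 | 38.4 | 0.80 | 50 |
| 5% | about 5 | 37.2 | 0.79 | 52 |
| 10% | about 10 | 35.3 | 0.77 | 55 |

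If the losses fall within the 20%, planned power does not change. The figures are for one dose comparison, as in the plan's own calculation.

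**4. R33.** The primary outcome is the self-report ZAN-BPD total (C.3.3), which needs no scan. A patient without a baseline scan can still contribute to it. Only the R33 imaging aims are exposed in the same way as R61.

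**The case against.** **Randomisation is not dated.** C.4.3.1 names the medical evaluation and allocation together, and the separate day could be read as separating the scan from the medical visit only. Allocation on the scan day is not ruled out. This stands in part: if that is already the practice, one sentence settles the point. As written, however, the only placement is with the medical evaluation.

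**Most screening comes first.** Candidates are screened before consent, and metal is checked at consent, so the later check should find only what is new or was missed. Withdrawal is attrition, which the 20% already covers. This stands, and is why the numbers are probably small.

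**Stronger readings that a reader might infer.** One is that staff who know the arm make the last eligibility decision, so that the R61 comparison is biased. The documents do not show this. F.1.2 does not name who makes the metal check. The C.2.5 experimenter must know the arm, but is not said to be the one checking, and metal and pregnancy leave little room for judgement. Another is that pregnancy exclusions are applied after allocation. The text is silent on the timing, which supports neither order.

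**A later call does not catch everything.** Claustrophobia and motion appear only in the scanner, after allocation. This stands, and calls for a reporting rule as well as a change of order.

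**Conclusion.** The point holds as a cheap improvement of low to moderate severity. On the order given in C.4.3.1, patients lost between allocation and the baseline scan are randomised but cannot enter the R61 PINES comparison, and the plan has no rule for them. The loss of power is small: from 0.81 to between 0.80 and 0.77 if an assumed 2% to 10% are lost beyond the 20% allowance, and nothing if they fall within it. Selection bias remains a possibility that the documents neither show nor exclude, and it cannot be sized from them. The R33 primary outcome is largely unaffected. The conclusion rests on reading C.4.3.1 as placing allocation at or about the medical evaluation. The planned sample sizes are not in dispute.

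**What to change.** In C.4.3.1, place the call to the online randomisation system at the baseline-scan visit. Make it once the laboratory and drug-screen results, the pregnancy test and a metal check on arrival have been signed off, and immediately before the arm-specific script. Keep the existing check just before scanning as a safety step. Patients who fail or withdraw earlier are then screen failures and are not randomised.

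In C.5 or C.6, add that any randomised patient who still has no usable baseline scan, for example through claustrophobia or motion, is reported by arm with the reason. This is needed in any case, because the arm-specific task means that randomisation cannot follow the scan.

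Cost: the metal check is made slightly earlier or repeated, and staff learn the allocation only on the scan day. No new visit or patient is needed, and 49 recruited and 39 analysable per arm stand unchanged.

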Analysis of the behavioral data demonstrated a decrease from baseline to session 5 in negative valence ratings in the BPD group in the Look-Negative as well as the Reappraise-Negative condition, suggesting the possibility that the effect of reappraisal training carried over to the Look condition, even without conscious intention. This observation is particularly encouraging in terms of *training generalizability*, since it suggests that training in distancing may facilitate its *automatic engagement*, without need for deliberate intent. We found (see fig 7) that the total negative valence ratings for RNeg and LNeg showed a significant decrease post-training (p< 0.05, twotailed). In terms of neural activity, we hypothesized that effective reappraisal of negative affective pictures would result in a downregulation of activity in a network known to

represent a sensitive and specific neural signature responsive to viewing aversive negative pictures, the PINES network [33]. We found that, as expected, after reappraisal training BPD patents showed decreased PINES activity when reappraising (vs. looking) relative to pretraining, with a large effect size (d=0.73, p<0.03, one-tailed; see Fig. 8). Thus, we found that with 5-days of reappraisal-by-distancing training BPD patients were able to significantly improve their ability to downregulate activity in the brain

network activated by negative emotion, and behaviorally to reduce how negatively they rated aversive pictures.

C.2. Overall Design

The present proposal follows the R61/R33 experimental medicine model to refine and test a proposed clinical intervention for BPD patients, training in reappraisal-by-distancing, in terms of its ability to influence hypothesized neural and behavioral targets and, once that is established, to demonstrate its ability improve clinically relevant outcome measures.

C.2.1. R61 Phase. Specifically, in the R61 phase we will determine whether reappraisal training will have an effect upon hypothesized proximal neural targets (see below) and behavioral measures (assessed by means of our imaging task; **C.2.6.**), further develop our treatment manual and will test 3 doses of the treatment with BPD patients -- treatment delivered 2 times a week for 2, 4 and 6-weeks. The reappraise-treatment condition will be contrasted with a control condition (**C.2.7.2**). Therapist's adherence to the manual will be assessed.

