neutral pictures, 2) look at negative pictures, and 3) regulate reactions to negative pictures. Each picture will be shown for 10 seconds and preceded with an instruction ("Look" or "Regulate"), which will appear on the screen for 2 seconds. Subjects will be told that when they see the "Regulate" instruction, they should employ reappraisal-by-distancing (treatment group) or *downregulate* (active control group). The "Look" instruction will be paired with neutral and negative pictures; "Regulate" with negative pictures only, since an instruction to emotionally down-regulate reactions to neutral pictures would be confusing. The order of the instruction/picture pairings will be randomized. Each picture is followed by a rating screen at which time subjects rate the valence of their reaction to the picture after carrying out the instruction on a 9-point scale (from -4 to 4) using an fMRI compatible slider. The rating screen will appear for 4 sec followed by an inter-trial screen that will be present for a jittered 2 – 6 sec. There will be 40 trials for each of the 3 conditions for a total of 40 minutes, divided into 4 runs of 10 minutes each.

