C.6.1 Image Acquisition. Participants will all be scanned 4 times in the R61 Phase (0, 2, 4, 6 weeks) or 2 times in the R33 Phase (Baseline, End-of-Treatment [EOT]) using the same 3 Tesla Siemens Skyra MRI system equipped with a 16-channel head coil. For each scan session, 4 series of 550 T2*-weighted images will be acquired during the 4 runs of the emotion regulation task using a multi-band echo-planar imaging sequence sensitive to the blood oxygenation level-dependent (BOLD) signal (multi-band factor = 7; repetition time = 1200 ms; echo time = 35 ms; flip angle = 60° ; field of view = 228 mm²; matrix = 108×108 ; slice thickness = 2.1 mm; 70 slices). A high-resolution anatomical image will be acquired with a T1-weighted magnetization-prepared rapid gradient echo (MP-RAGE) sequence.

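### Aim R61-2c negative-affect model: with no participant-level Trial Type term, Group x Trial Type is too liberal and, on cell means, the three-way training contrast too conservative, if participants differ

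*Combined protocol and SAP*

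**What the plan says.** Section C.5.1 (Aim R61-2c) plans linear mixed models with fixed effects for Training Group, Session and Trial Type (Look Neutral, Look Negative, Regulate Negative) and their interactions, "as well as a random effect consisting of an intercept for each participant". It then adds: "We will examine additional models that incorporate and estimate random-effects slope variance across participants on the time effect (i.e., Session". It names no participant-level Trial Type term, residual covariance structure or robust standard error.

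There are two outcomes: self-reported negative affect, and "reappraisal success (defined as the Look Negative minus Regulate Negative behavioral valence rating at each Session". The second is already a difference between trial types, so Trial Type is not a factor for it.

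On the data, C.2.5 states "There will be 40 trials for each of the 3 conditions" and C.6.1 states "Participants will all be scanned 4 times in the R61 Phase (0, 2, 4, 6 weeks) or 2 times in the R33 Phase". Section C.5.1 does not say whether single trials or cell means are analysed. For Aim R33-2, C.5.2 says: "The analysis will be as for R61 Aims R61-2 a,b and c".

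Section C.3.3 makes change in PINES activity the R61 primary outcome. The ratings are among the other outcomes.

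**The concern.** A participant intercept assumes that, apart from overall level, every participant in an arm shares the same difference between trial types. That is a strong assumption here. Control participants are told that "they should use whatever emotion regulation strategy works for them to reduce their negative feelings" (C.2.5), and C.2.6.2 concedes that the control condition is heterogeneous.

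If reactivity or regulation differs between people, that variation belongs in the error term for Group x Trial Type. The planned model pools it with smaller components, so this test rejects too often. On cell means the same pooling puts the variation into the error term of the three-way contrast, where it does not belong, and that test loses power.

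Two results are at stake. A chance Group x Trial Type difference could be reported as real. A null three-way result could also stand beside a significant success-score result from the same ratings.

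**Working it through.** **The plan's own figure.** Section C.7 powers R61 on PINES with d = .65, two-sided alpha .05 and power .80. Noncentral-t power is .799 at 38 per group and .809 at 39, so 39 is reproduced. The plan states no power or error rate for the ratings model.

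**Inputs.** From the documents: 39 per arm, 4 sessions and 3 trial types in R61; 51 per arm and 2 sessions in R33; two-sided alpha .05. Assumed, because the documents give no variances: cell-mean residual SD s_e = .5, and participant-by-session SD s_ps equal to participant-by-type SD s_pt, at 0, .1, .3 or .5.

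**Error terms, R61 cell means.** Within participants there are 3 df for session, 2 for type and 6 for session-by-type, 11 in all. Expected mean squares are s_e² + 3s_ps², s_e² + 4s_pt² and s_e².
- Pooled residual, intercept only: s_e² + (9s_ps² + 8s_pt²)/11, on 76 × 11 = 836 df.
- Correct error for Group x Trial Type: s_e² + 4s_pt².
- Correct error for the three-way term: s_e².

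**Group x Trial Type.** The joint test has 2 numerator df and critical F of about 3.01, so its null error is close to exp(−3.01 × pooled/correct). At SD .3: pooled = .25 + 17 × .09/11 = .389; correct = .25 + .36 = .61; exp(−3.01 × .638) = .147.

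**Three-way contrast** (Regulate versus Look Negative, week 6 versus baseline). The true SE is sqrt(4 × .25 × 2/39) = .226. The model rejects beyond 1.963 × sqrt(4 × pooled × 2/39). The effect is set at .64 points, which gives the success score 80% power.

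**Success score.** The week 6 minus baseline change in the success score is the same estimate. Stable participant-by-type effects and participant-by-session effects both cancel from it. Its change variance is 4 × .25 = 1.0, so its power stays at 80%.

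| SD | Pooled | Correct for Group x Type | Group x Type error | Three-way critical difference | Three-way power | Success-score power |
|---|---|---|---|---|---|---|
| 0 | .250 | .250 | 5% | .444 | 80–81% | 80% |
| .1 | .265 | .290 | 6% | .458 | 78–79% | 80% |
| .3 | .389 | .610 | 15% | .555 | 64% | 80% |
| .5 | .636 | 1.250 | 21–22% | .709 | 38% | 80% |

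Simulation agrees with the formulas. With this effect, the success score is significant and the three-way test is not in about 1/2/16/42% of trials.

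**Planned Session slope.** The pooled residual becomes s_e² + (6s_ps² + 8s_pt²)/10 if session variation is irregular, or s_e² + 8s_pt²/10 if it is linear. Group x Trial Type error at .1/.3/.5 is then 7/16/24% or 7/21/34%. A Session slope cannot absorb a Trial Type effect.

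**R33.** The pooled residual is s_e² + (3s_ps² + 4s_pt²)/5, against a correct s_e² + 2s_pt². At .3 this is .376 against .430. Group x Trial Type error is 5/7/9% at .1/.3/.5, and three-way power is 79/66/42%.

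**Single trials** (assumed trial SD 1.5). With a stable participant-by-type SD of .25, Group x Trial Type error is about 57% and the three-way test stays near nominal. If the Trial Type effect also varies by session within participant, with SD .1 or .25, three-way error rises to about 8–9% or 34–42%.

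**A smaller effect.** Section C.2.2 reports the earlier behavioural effect as d = 0.15. With a between-arm effect of .15 on the change SD of 1.0, success-score power is about 10%. The success score alone is significant in about 1% of trials or fewer at SD 0, then about 1/6/10% at .1/.3/.5.

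**Check on the remedy.** Participant-by-type and participant-by-session terms with one common residual variance are not enough if Look Neutral ratings vary less. With an assumed Look Neutral SD of .2 against .5 for both negative types, the pooled interaction variance is (.04 + .25 + .25)/3 = .18, where .25 is needed. The critical value shrinks to 1.965 × sqrt(.18/.25) = 1.67, a null error of about 10%. At SD .3 it is about 8%. The success score stays near 5%.

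**The case against.** The strongest reply is that the inflated test is not the training test. Group x Trial Type averages over all sessions, including the untrained baseline scan. Training is a change over sessions, carried by the three-way contrast or the success-score Group x Session test. The first is conservative on cell means and the second is calibrated. This stands. A reader might infer that the plan is prone to false claims of a training effect. On cell means that would require misreading Group x Trial Type.

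A second reply is that the plan already leans towards the success score: A.3 glosses the predicted fall in ratings as improved reappraisal success, and B and C.2.1 name reappraisal success as the behavioural target. This stands in part. Section C.3.3 lists valence ratings during reappraisal instead, C.5.1 ranks neither outcome, and the document refers to Aim R61-2c by label without giving its wording.

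A third reply is that the sizes are assumed. This stands too. Equal session and type SDs are a convenience, and an effect of .64 is far above the earlier d = 0.15. That figure is a training effect from the earlier study rather than a between-arm effect, but it is the only behavioural one given. The direction on cell means does not depend on the SDs chosen, provided participants differ stably between trial types.

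**Conclusion.** The concern holds within limits. If participants differ in reactivity or regulation, the negative-affect model uses the wrong error terms: too small for Group x Trial Type and, on cell means, too large for the three-way contrast. The planned Session slope does not cure this. Under the assumed SDs the consequence runs from small (.1) to substantial (.5). With an effect near d = 0.15, power is low for every test and the two training tests disagree less often.

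Three stronger readings are not supported:
- That the three-way test is inflated. On cell means it is conservative. On single trials it is liberal only if the Trial Type effect also varies by session within participant.
- That the success score shares the fault. The missing Trial Type term does not touch it.
- That the R61 go decision or sample size is compromised. Both rest on PINES, so the milestone and n = 39 are unaffected.

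This is a low-severity point on a secondary outcome, worth correcting because Aim R33-2 reuses the model.

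**What to change.** 1. Name the success-score Group x Session test, fitted with the planned Session slope or an unstructured covariance, as the deciding behavioural test of training. This agrees with A.3, B and C.2.1.
2. Keep the negative-affect model as supporting, and state whether cell means or single trials are analysed. It still has a role: the earlier study saw a fall "in negative valence ratings in the BPD group in the Look-Negative as well as the Reappraise-Negative condition" (C.1.3.3), and a difference score cancels a change common to both conditions.
3. In that model, allow for participant-level Trial Type variation without assuming equal variance across trial types. Either use participant-clustered, small-sample-corrected standard errors, or add participant-by-trial-type and participant-by-session random terms with trial-type-specific residual variances. For single trials, also add a participant-by-session-by-type term. In R33, with two scans, the Session slope and the participant-by-session term coincide, so keep one.
4. State that Group x Trial Type will not be read as evidence of a training effect.

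The cost is SAP wording and slightly more complex fitting, with no change to data collection or sample size. The larger random-effects model carries some risk of non-convergence; clustered standard errors are the fallback.
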